## 8. PHARMACOKINETIC ANALYSIS

### 8.1 Pharmacokinetic Parameters

The PK parameters will be derived and estimated based on measured teduglutide plasma concentrations using Non-compartmental analysis (NCA) by a Takeda designated vendor in accordance with the PK SAP and generated separately.

### 8.2 Statistical Analysis of Pharmacokinetic Data

The PK concentration data will be summarized on the PK Population for the protocol scheduled sampling time points:

At Baseline:

- 0 hour (predose) draw: any time prior to the dose
- 15 minutes postdose  $\pm 5$  minutes
- 30 minutes postdose  $\pm 5$  minutes
- 1 hour postdose  $\pm 10$  minutes
- 2 hours postdose  $\pm 10$  minutes
- 3 hours postdose  $\pm 10$  minutes
- 4 hours postdose  $\pm 30$  minutes
- 6 hours postdose  $\pm 30$  minutes
- 8 hours postdose  $\pm 30$  minutes

Document: T:\PROJ\Shire\UYA25606\_Biostatistics\Documentation\SAP\SAP\SHP633-306\_SAP\_Final  
v2.0\_20180415.docx

Author: [REDACTED]

Version Number:  
Version Date:

Final V2.0  
15Apr2019

- 10 hours postdose  $\pm$ 30 minutes
- 12 hours postdose  $\pm$ 30 minutes

At Week 4 or Week 12:

- 0 hour (predose) draw: any time prior to the daily dose, on the day of dosing, but at least 14 hours after the previous dose
- 1 hour postdose  $\pm$ 10 minutes
- 2 hours postdose  $\pm$ 10 minutes

Descriptive statistics of PK concentration (number of subjects, mean, standard deviation, coefficient of variation (CV) %, geometric mean, geometric CV (%), median, minimum and maximum values) will be calculated at each time point. Mean ( $\pm$ SD) PK concentration by time curves will be provided for the PK population. PK concentration by time will also be plotted by individual subject. A listing for PK concentration data will also be provided.

## 9. OTHER ANALYSES

The information related to the study drug training provided by the study physician will be listed for all subjects in the Safety Population.

## 10. INTERIM ANALYSIS/ DATA MONITORING (REVIEW) COMMITTEE

Interim analyses may be conducted during the study, as needed. Analyses will be descriptive in nature. No formal comparisons are planned, and no hypotheses will be formally tested. Due to the open-label nature of this study, personnel involved in conducting the interim analyses will have access to treatment assignments.

## 11. DATA HANDLING CONVENTIONS

### 11.1 General Data Reporting Conventions

The small sample size resulting from the small study population requires the use of descriptive statistics with a goal of summarizing the sample and thus discourages the use of inferential statistics.

Data from all healthcare setting study sites that participate in this protocol will be combined so that an adequate number of subjects will be available for analysis.

Document: T:\PROJ\Shire\UYA25606\_Biostatistics\Documentation\SAP\SAP\SHP633-306\_SAP\_Final  
v2.0\_20180415.docx

Author: [REDACTED]

Version Number:

Final V2.0

Version Date:

15Apr2019

Descriptive statistics will be presented as follows:

- Continuous variables, including those assessed on a discrete scale, will be summarized using the following descriptive statistics: the number of subjects, mean, median, standard deviation, minimum, maximum and 95% confidence interval where needed. The standard errors will be calculated in the tables if a corresponding figure is generated (e.g., efficacy tables).
- Categorical variables will be summarized by the number and percentage of subjects in each category (with a category for missing data as needed). Unless otherwise stated, the denominator for percentages is N (the number of subjects in the analysis population).

The following rules will be followed for decimal places and rounding:

- Unless otherwise specified, means (arithmetic and geometric) and medians will be rounded and presented to 1 decimal place more than the raw data and standard deviations to 2 decimal places more than the raw data. Minimum and maximum values will be presented to the same number of decimal places as the raw data.
- Unless otherwise specified, percentages should be presented to one decimal place. Less than signs (i.e., '<') should be presented as appropriate (e.g., 0.04% should be presented as < 0.1%, not 0.0%). This rule also applies to %CV.
- BMI, duration of SBS and years since start of PN dependency should be rounded to 1 decimal place for reporting.

Study day will be calculated as follows;

- If the evaluation date is on or after the date of first day of study medication:

$$\text{Study day} = \text{date of evaluation} - \text{first day of study medication} + 1$$

- If the evaluation date is before the date of first day of study medication:

$$\text{Study day} = \text{date of evaluation} - \text{first day of study medication}$$

All output should have a 3-line header at the upper left margin:

Document: T:\PROJ\Shire\UYA25606\_Biostatistics\Documentation\SAP\SAP\SHP633-306\_SAP\_Final  
v2.0\_20180415.docx

Author: [REDACTED]

Version Number:

Final V2.0

Version Date:

15Apr2019

Takeda  
SHP633-306  
Confidential

All output should have a 1-line footer with the SAS program name, including the path, and the date and time the output was produced at the lower left margin of the footer.

Tables and listings should be internally paginated in relation to the total length for that table or listing (i.e., Page n of N, where n is the page number within the table or listing and N is the total number of pages for that table or listing).

The table, figure and listing numbering will be based on the International Conference on Harmonization (ICH) guidelines.

A number should identify each table/listing, and the table designation (e.g., Table 14.x) should be centered above the title. A decimal system (e.g., x, x.y, x.y.z) should be used to identify tables/listings with related contents. The title should be centered and in mixed-case characters. The title and table/listing designation should be single-spaced but are separated from the content of the table/listing by a space and a solid underline. The study population and/or subgroup (e.g., ITT Population) should be identified on the line immediately following the title.

Column headings should be in title case characters. For numeric variables, the unit should be included in the column heading when appropriate.

Footnotes should be single spaced but separated by an underline and a space from the text of the table/listing. The notes should be aligned vertically by the left vertical border of the table/listing. Numeric references, which can be confused with data, should not be used. Rather asterisks and other non-numeric symbols should be used to refer to footnotes.

The dictionary (e.g., MedDRA, WHODD) and the dictionary version numbers should be identified in the footnotes to the tables/listings for data coded with a dictionary.

For both tables and listings where there are no observations (and hence there would be no output), the table/listing should be produced with all titles and footnotes as per its shell, but with the text showing no observations in the body of the output.

Document: T:\PROJ\Shire\UYA25606\_Biostatistics\Documentation\SAP\SAP\SHP633-306\_SAP\_Final  
v2.0\_20180415.docx

Author: [REDACTED]

Version Number:  
Version Date:

Final V2.0  
15Apr2019

Individual data listings will be sorted and presented by subject number and visit/event date.

Dates will be presented in a DDMONYY format. Dates with partial missing data will be presented with a dash (i.e., '-') for the missing data (e.g., --JAN2019).

In general, analyses on PP population will be conducted if PP population is different from ITT population.

For the following analyses, data for ITT, PP and Safety will be presented side by side in tables:

- Demographic and other baseline characteristics
- Short bowel syndrome history
- Parenteral nutrition history
- Crohn's disease evaluation
- Gastrointestinal specific testing
- Exposure of investigational product
- Treatment compliance

## 11.2 Definition of Baseline

For summary purposes, the baseline value will be defined as the last available pre-dose value.

## 11.3 Definition of Visit Windows

Although there is a visit window from 2 to 7 days around the expected visit date, nominal visits will be used for the per-visit analyses. Therefore, no windowing of visits by actual study day will be done for data obtained at the scheduled visits. For subjects who withdraw from the study pre-maturely, if the ET visit falls into the window of a scheduled visit as defined in the protocol, the ET visit is also summarized for that scheduled visit, unless the scheduled visit already took place.

Document: T:\PROJ\Shire\UYA25606\_Biostatistics\Documentation\SAP\SAP\SHP633-306\_SAP\_Final  
v2.0\_20180415.docx

Author: [REDACTED]

Version Number:  
Version Date:

Final V2.0  
15Apr2019

## 11.4 Derived Efficacy Endpoints

An EOT time point, defined as the last determination of endpoint or last available measurement from the date of first dose, will be analyzed in addition to the scheduled visits. Unscheduled measurements will not be included in by-visit summaries but can contribute to the EOT value where applicable.

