^j Blood sample for antibody testing is to be collected at baseline (Visit 2) prior to first investigational product administration. Blood samples for antibody testing at Week 12 (Visit 7) and Week 24 (Visit 10) must be collected prior to that day's dose, and more than 14 hours after the prior day's dose.

^k Samples for PK analysis will be collected pre-dose and at 15, 30 minutes post-dose and at 1, 2, 3, 4, 6, 8, 10 and 12 hours post-dose at Visit 2. Additional PK samples will be collected predose, and 1 and 2 hours post-dose at Week 4 (Visit 5) or Week 12 (Visit 7). The site of teduglutide administration prior (arm, thigh, or abdomen) and the person administering the injection (subject or physician) must be specified. Blood sample for measuring PK must be drawn from peripheral venous access.

^l For women of childbearing potential.

^m Teduglutide is dosed once daily during the treatment period. The first dose of study drug must be administered by the study physician.

ⁿ Dosing will continue if the subject enters the extension study, but will stop at the Week 24 visit if the subject doesn't enter the extension study.

^o The study physician must observe the subject administering the study drug in compliance with the study drug administration checklist at least twice before the subject is allowed to administer the drug without direct observation by the physician. Refer to Section 6.2.2.1.

^p For subjects entering the extension study only.

^q Interim safety evaluations will be performed 5 to 7 days after any change to the subject's PN/IV has been implemented. These measures include 48-hour oral fluid intake, 48-hour urine output, hemoglobin, hematocrit, serum blood urea nitrogen, creatinine, and urine sodium, and may be performed at the investigational site laboratory.

^r Subjects will record their PN/IV support and teduglutide dosing daily throughout the study. Prior to each clinic and safety visit, subjects will also record all enteral fluid intake and urine output over a 48-hour period.

^s Compliance will be checked at every visit by asking subjects if they have taken their study drug according to instructions and by performing drug accountability.

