7.2.4 Pharmacokinetic Assessments

The first dose of teduglutide will be administered by the study physician at the baseline visit (Visit 2). At this visit, subjects will have blood samples taken for teduglutide PK analysis:

- 0-hour (predose) draw: any time prior to the dose
- 15 minutes postdose: ± 5 minutes
- 30 minutes postdose: ± 5 minutes
- 1 hour postdose: ± 10 minutes
- 2 hours postdose: ± 10 minutes
- 3 hours postdose: ± 10 minutes
- 4 hours postdose: ± 30 minutes
- 6 hours postdose: ± 30 minutes
- 8 hours postdose: ± 30 minutes
- 10 hours postdose: ± 30 minutes
- 12 hours postdose: ± 30 minutes

Subjects also will have blood samples taken for teduglutide PK analysis at Week 4 (Visit 5) or Week 12 (Visit 7):

- 0-hour (predose) draw: any time prior to the daily dose, on the day of dosing, but at least 14 hours after the previous dose
- 1 hour postdose: ± 10 minutes
- 2 hours postdose: ± 10 minutes

Blood for PK sampling should be collected via peripheral IV or venipuncture, not from a central line. The site of teduglutide administration prior to PK blood draws (arm, thigh, abdomen) and the person administering the injection (physician or subject) must be recorded in the eCRF.

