### 2.2 Estimand(s)

Absolute change from baseline in weekly PN/IV volume based on diary data at End of Treatment (EOT) in Japanese subjects with PN/IV – dependent SBS in the Intent-to-treat (ITT) Population.

Relative change from baseline in weekly PN/IV volume based on diary data at EOT in Japanese subjects with PN/IV – dependent SBS in the ITT Population.

Number/percentage of subjects who achieved at least 20% decrease from baseline in weekly PN/IV volume based on diary data at Week 20 and Week 24 in Japanese subjects with PN/IV – dependent SBS in the ITT Population.

Number/percentage of subjects who achieved at least 20% decrease from baseline in weekly PN/IV volume based on diary data at Week 20 and Week 24 in Japanese subjects with PN/IV – dependent SBS in the PP Population.

Number/percentage of subjects who achieve at least a 20% reduction from baseline in weekly PN/IV volume based on diary data at each visit in Japanese subjects with PN/IV – dependent SBS in the ITT Population.

Document: T:\PROJ\Shire\UYA25606\_Biostatistics\Documentation\SAP\SAP\SHP633-306\_SAP\_Final  
v2.0\_20180415.docx

Author: [REDACTED]

Version Number:  
Version Date:

Final V2.0  
15Apr2019

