## 6.1 Analyses of Efficacy Endpoints

The efficacy endpoints are the following:

- Absolute and relative change from baseline in weekly PN/IV volume by visit and at EOT.
- Percentage of subjects who achieve at least 20% reduction from baseline in weekly PN/IV volume at both Weeks 20 and 24.
- Percentage of subjects who achieve at least a 20% reduction from baseline in weekly PN/IV volume at each visit
- Change in days per week of PN/IV support from baseline by visit.
- Change in plasma citrulline from baseline by visit.
- Number of subjects who were able to completely wean off of PN/IV support.

Analyses on weekly PN/IV support are based on two data sources: the subject diary data and the investigator prescribed data.

The diary weekly PN/IV volume will be calculated based on the daily volumes recorded in subjects' diaries within 14 days prior to each scheduled visit. The calculation will follow the formula below.

Weekly volume = (sum of daily volumes in the diary/number of days with values) \*7

Missing daily PN/IV volumes will not be imputed. A maximum of 5 missing days (or at least 9 days of non-missing data) from the 14-day intervals are allowable, otherwise the interval will be classified as missing. One exception to this rule is the baseline interval, which will be filtered back up to 28 days prior to first dose until 9 data points are obtained.

Investigator prescribed data is captured in the PN/IV baseline and PN/IV adjustment in eCRF. Investigator prescribed weekly PN/IV volume reported at each visit will be the most recent PN/IV prescription (from either baseline or prescription adjustments) prior to or on the date of visit.

Data will be summarized at all scheduled visits during the 24-week treatment period. An EOT time point will also be added. Therefore,

Document: T:\PROJ\Shire\UYA25606\_Biostatistics\Documentation\SAP\SAP\SHP633-306\_SAP\_Final  
v2.0\_20180415.docx

Author: [REDACTED]

Version Number:  
Version Date:

Final V2.0  
15Apr2019

- PN/IV weekly volume and days per week of PN/IV support will be summarized at Baseline, Weeks 2, 4, 8, 12, 16, 20, 24 and EOT.
- Plasma citrulline will be summarized at Baseline, Weeks 4, 8, 16, 24 and EOT.

Datasets and listings will include data collected at unscheduled visits. Data collected at unscheduled visits will not be included in summaries by timepoint or visit unless specified otherwise.

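### SAP 11.4 sets EOT by date, so a pre-dose Visit 2 value could be reported as end of treatment for a dosed subject with no later value of that parameter

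*SAP*

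**What the plan says.** All SAP references are to v2.0.

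- **EOT.** Section 11.4 adds an EOT time point, "defined as the last determination of endpoint or last available measurement from the date of first dose". Unscheduled measurements may supply it. The bound is a date, with no requirement that the value be post-dose or post-baseline.
- **Baseline.** Section 11.2 says "the baseline value will be defined as the last available pre-dose value".
- **First dose.** Protocol 7.2.4 says "The first dose of teduglutide will be administered by the study physician at the baseline visit (Visit 2"). The date of first dose is therefore the date of Visit 2.
- **Same-day pre-dose samples.** A footnote to Protocol Table 2 says "Blood sample for antibody testing is to be collected at baseline (Visit 2) prior to first investigational product administration".
- **Where EOT is reported.** SAP 6.1 says "Plasma citrulline will be summarized at Baseline, Weeks 4, 8, 16, 24 and EOT". EOT is also a column for laboratory tests (7.2), vital signs, weight and BMI (7.3) and antibodies (7.5.2). Section 11.4 is headed for efficacy, but it holds the SAP's only definition of EOT.
- **Missing data.** Section 11.5 rules out imputation, naming last observation carried forward, except for partial dates.

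**The concern.** A rule that starts on the first-dose date takes in everything measured at Visit 2, including what was measured before the injection. For most subjects this does no harm, because a later value supersedes it. For a subject with no later value of a parameter, the Visit 2 value is the only candidate, and it is also that subject's baseline.

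The summary could then show an end-of-treatment result for someone never assessed on drug for that parameter. Its change of zero would come from the definition and not from observation. The mean change would move toward zero, and n would overstate how many subjects were evaluated after exposure. With about 5 treated subjects, one record is visible in the table.

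**Working it through.** The plan gives no figure to reproduce. The check is a reading of the rules by data type, followed by simple arithmetic.

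**Step 1: does a pre-dose Visit 2 value meet the EOT wording?** Yes, literally. Its date equals the first-dose date. The study-day convention in SAP 11.1 points the same way: any evaluation on or after the first-dose date gets +1, so a pre-dose Visit 2 value falls on Study Day 1. Elsewhere the SAP does deal with the same-day problem. Section 7.1 uses time of onset for adverse events dated on the first-dose day, and 7.2 limits markedly abnormal laboratory values to those after baseline. Section 11.4 has neither safeguard.

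**Step 2: which data types are exposed?** Take a dosed subject with no later value.

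| Data | Pre-dose at Visit 2? | First later summary | Literal EOT |
|---|---|---|---|
| Antibodies | Stated (Table 2 footnote) | Week 12 | Pre-dose sample counted; no change score |
| Weight | Implied: the baseline weight enters the dose calculation | Week 2 | Baseline, change 0 |
| Citrulline | Inferred | Week 4 | Baseline, change 0 |
| Laboratory tests, vital signs | Inferred | Week 2 | Baseline, change 0 |
| Diary PN/IV volume | No; see step 3 | Week 2 | Missing |

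**Step 3: why diary volume is outside the problem.** SAP 6.1 computes it from "daily volumes recorded in subjects' diaries within 14 days prior to each scheduled visit". The baseline interval is one "which will be filtered back up to 28 days prior to first dose until 9 data points are obtained". Those diary days precede the first-dose date and fall outside the EOT bound. The value would be missing, not zero, unless a programmer stamped the derived baseline record with the Visit 2 date.

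**Step 4: responder percentages.** The Week 20 and 24 responder endpoint does not use EOT. For response at EOT, the SAP 11.1 denominator is N, so a zero change and a missing value both leave the responder count and the percentage as they were.

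**Step 5: size for an exposed parameter.** If k of n subjects contribute a zero and the other n − k average m, the reported mean is m × (n − k)/n.

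| n | k = 1 | k = 2 |
|---|---|---|
| 5 | 4/5 = 0.80 | 3/5 = 0.60 |
| 6 | 5/6 = 0.83 | 4/6 = 0.67 |
| 7 | 6/7 = 0.86 | 5/7 = 0.71 |

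Example with an assumed change, not taken from the documents: four subjects average +10 units and one contributes 0. The mean is (4 × 10 + 0)/5 = +8 with n = 5, against +10 with n = 4 if that subject is missing. In the antibody table the effect is on a count: 5 samples analysed at EOT where 4 were taken on treatment.

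**The case against.** The strongest reply is that the SAP, read as a whole, leaves EOT missing in this case. Section 11.2 gives the last pre-dose value the role of baseline, an end-of-treatment time point would naturally mean something after treatment began, and 11.5 forbids carrying values forward. The table specifications are in a separate document and may already handle it. This stands to the extent that the false zero is permitted, not compelled. It does not remove the gap, because nothing in 11.2 to 11.5 expressly excludes a Visit 2 pre-dose value from EOT. The result would depend on which section the programmer followed.

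The second reply is that the trigger is rare. Protocol 4.4 asks for the Visit 10 evaluations, as far as they can be done, whenever drug is stopped. Table 2 repeats this for early-termination visits, and unscheduled values can also supply EOT. For laboratory tests, weight and vital signs, a subject would need no usable value at Week 2 or at any later visit. This also stands, and it keeps the point minor.

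A reader might infer that the main EOT estimands are biased, since SAP 2.2 sets PN/IV volume change at EOT. The documents do not support that: those estimands use diary data, and step 3 shows the baseline diary days lie before the bound. For prescribed volume, the SAP reports the prescription in force. If it was never adjusted, a zero change is a true statement.

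**Conclusion.** The wording gap is real, and it is minor. As written, 11.4 allows a pre-dose Visit 2 value to serve as both baseline and EOT for a dosed subject who has no later value of that parameter from any source. Where this happens, one subject in 5 reduces the mean EOT change for that parameter by 20%, or adds one pre-dose antibody sample to the EOT count.

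It would be too strong to say that the plan requires this result, that it touches the diary-based volume estimands, or that it alters the responder percentages.

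The conclusion rests on three assumptions:

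- Citrulline, laboratory tests and vital signs are measured at Visit 2 before dosing. The body of Table 2 is not in the available text, so this is inferred. Antibody timing is stated.
- The EOT definition in 11.4 also governs the safety tables, which offer no other definition.
- At least one dosed subject lacks any later value. If none does, nothing changes.

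**What to change.** In 11.4, define EOT as the last available measurement taken after the first dose, judged by date and time. Where the time is missing, require a visit after Visit 2. State that EOT is missing when no such measurement exists, and that the definition applies to the safety tables as well. This brings 11.4 into line with 11.5 and loses no valid post-dose data. The cost is one phrase in the SAP, and n at EOT may be one lower for some parameters.

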## 11.5 Handling of Missing, Unused, and Spurious Data

No imputation for missing data (e.g., last observation carried forward) will be applied except for the partial dates to derive treatment emergent adverse events and flagging prior/concomitant medications.

Imputation will be performed for partial dates of AEs and medications solely for the purpose of defining treatment emergence for AEs, determining whether an AE started in the treatment period and prior/concomitant status for medications. Details on how to handle partial dates for adverse events and prior/concomitant medications are described below.

